### **10.6.1.2 Safety Laboratory**

Laboratory values will be graded by NCI CTCAE version 4.03, if no grading exists values will be classified into low/normal/high based on laboratory normal ranges. Each parameter will be presented by descriptive statistics at each visit including change from baseline (screening). Shift tables for CTCAE grades and normal ranges will be presented. All laboratory values will be listed. A separate listing for abnormal lab values (Grade 3 and higher, and low/high values) will be presented.

### **10.6.1.3 Vital Signs**

Vital signs will be summarised by descriptive statistics at each visit including change from baseline will be presented and a listing will be provided.

### **10.6.1.4 Electrocardiogram**

Centrally read ECG data will be listed overall and a separate listing for any clinically significant finding in ECG values will be provided. Change from baseline in QT intervals by cohort will be summarised for each visit as well as change from baseline in all other ECG parameters. Also, the worst change from baseline will be summarised. The frequency and percentage of patients with notable ECGs and newly occurring qualitative ECG abnormalities will be tabulated by cohort.

## **10.6.2 Efficacy Analyses**

### **Overall response rate:**

For solid tumours, overall response rate as defined by achieving confirmed complete response (CR) and/or partial response (PR) will be presented by percentage rates and 95% confidence intervals. For changes in solid tumour size waterfall plots will be

presented. For all response assessments, swimmers plots will be presented. All response assessments will be listed.

In T-ALL/T-LBL, overall response rate defined as achieving confirmed Complete Remission (CR) and/or Complete Remission with Incomplete Hematologic Recovery (CRi) will be presented by percentage rates and 95% confidence intervals (CI).

**Clinical benefit rate for solid tumours at Month 3, 6, and 9, and for T-ALL/T-LBL at 1, 2, and 3 months, and every 2 months from Month 3 to Month 9:**

Clinical benefit rate as defined by achieving complete response and/or partial response and/or stable disease (SD) will be presented by percentage rates and 95% confidence intervals. Waterfall plots will be presented.

- For solid tumour indications: Clinical benefit rate (CR + PR + SD), assessed by RECIST 1.1.

**Duration of response:** The duration of response defined as time from first assessment of PR or CR in solid tumours or CR/CRi in T-ALL/T-LBL to follow-on first assessment of PD or relapse will be summarised by descriptive statistics including median duration of response and respective 95% CIs. Duration of response will also be listed.

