### 4.2.2 Secondary Endpoints

The secondary endpoints for both Part A and B of this study are as follows, unless otherwise specified:

- The incidence rate, severity and relationship to CB-103 of adverse drug reactions and serious drug reactions according to common terminology criteria for adverse events (CTCAE) V4.03, safety laboratory, vital signs, ECG and ECHO/MUGA assessments in each dose group and expansion arm.
- CB-103 plasma concentrations, PK parameters:  $C_{max}$ ,  $t_{max}$ ,  $C_{min}$ ,  $C_{last}$ ,  $t_{last}$ , area under the curve (AUC) during 8 and 24 hours ( $AUC_{0-8}$ ,  $AUC_{0-24}$ ), AUC from time 0 extrapolated to infinite time ( $AUC_{0-\infty}$ ), apparent volume of distribution ( $V_d/F$ ), apparent volume of distribution at steady ( $V_{ss}/F$ ), apparent clearance after oral administration ( $CL/F$ ),  $t_{1/2}$  and AR.
- **Part A only:** to assess tumour response rates
  - For solid tumour indications: to assess best overall response rate (CR + PR), assessed by RECIST 1.1 (Eisenhauer et al., 2009).
  - For haematologic malignancies: to assess the best overall response rate (CR or CRi) per NCCN guidelines.
- To assess clinical benefit rate

- For solid tumour indications: clinical benefit rate (CR + PR + SD), assessed by RECIST 1.1. (Eisenhauer et al., 2009).
- Duration of response (DOR), time to response, progression-free survival (PFS), OS.

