## **Appendix 8 Response Assessment in Acute Lymphoblastic Leukaemia/ Lymphoblastic Lymphoma**

### **Response criteria for Blood and Bone Marrow:**

- CR
  - No circulating lymphoblasts or extramedullary disease
  - No lymphadenopathy, splenomegaly, skin/gum infiltration/testicular mass/CNS involvement
  - Trilineage haematopoiesis (TLH) and <5% blasts
  - Absolute neutrophil count (ANC) >1000/microL
  - Platelets >100,000/microL
  - No recurrence for 4 weeks
- CR with incomplete blood count recovery (CRi)
  - Meets all criteria for CR except platelet count or ANC
- Overall response rate (ORR = CR + CRi)
- **NOTE:** MRD assessment is not included in morphologic assessment and should be obtained
- Refractory disease
  - Failure to achieve CR at the end of induction
- Progressive disease (PD)
  - Increase of at least 25% in the absolute number of circulating or bone marrow blasts or development of extramedullary disease
- Relapsed disease
  - Reappearance of blasts in the blood or bone marrow (>5%) or in any extramedullary site after a CR

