#### **5.6.2.4 Clinical Benefit Rate (CBR)**

Patients with solid tumours are considered to have clinical benefit if they have a tumour assessment status of CR, PR or SD according to RECIST, v1.1.

The CBR at 3 months, 6 months and 9 months after treatment start will be presented together with corresponding Clopper-Pearson 95% CI for each dose group with at least 6 patients.

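### Protocol section 10.6.2 schedules a clinical benefit rate for T-ALL/T-LBL but defines it as CR/PR/SD, which does not fit the Appendix 8 criteria and leaves out CRi

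*Protocol*

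**What the plan says.** The CBR heading in protocol section 10.6.2 gives T-ALL/T-LBL its own timetable: "and for T-ALL/T-LBL at 1, 2, and 3 months, and every 2 months from Month 3 to Month 9". That is months 1, 2, 3, 5, 7 and 9. The sentence below it reads "Clinical benefit rate as defined by achieving complete response and/or partial response and/or stable disease (SD) will be presented". One disease-specific bullet follows: "For solid tumour indications: Clinical benefit rate (CR + PR + SD), assessed by RECIST 1.1". There is no matching bullet for T-ALL/T-LBL.

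A little earlier, the same section defines response for this disease in other terms: "In T-ALL/T-LBL, overall response rate defined as achieving confirmed Complete Remission (CR) and/or Complete Remission with Incomplete Hematologic Recovery (CRi". Appendix 8 agrees. Its blood and marrow categories are CR, CRi, refractory disease, progressive disease and relapse. It describes CRi as "Meets all criteria for CR except platelet count or ANC" and gives the response rate as "Overall response rate (ORR = CR + CRi". Stable disease appears nowhere in Appendix 8. Partial response appears only under lymphomatous extramedullary disease, where the residual category is No Response.

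Other places restrict CBR to solid tumours. Protocol section 4.2.2 has "For solid tumour indications: clinical benefit rate (CR + PR + SD), assessed by RECIST 1.1", and SAP section 5.6.2.4 has "Patients with solid tumours are considered to have clinical benefit if they have a tumour assessment status of CR, PR or SD". SAP section 2.6 and the efficacy analysis text of the synopsis do the same.

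**The concern.** The stated definition is a RECIST definition attached to a disease that is not assessed by RECIST. Two of its three components do not exist for marrow disease, and one of the two categories that count as response in this disease is missing. A patient in CRi is then a responder who has no clinical benefit.

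T-ALL/T-LBL patients may enter both the Part A confirmatory cohort and a Part B arm, so the rate could be called for in either report. An analyst following 10.6.2 would either report a benefit rate that understates the remission rate or repair the definition after seeing the data. An analyst following section 4.2.2 would report no such rate.

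**Working it through.** The documents state no CBR figure for T-ALL/T-LBL, so there is nothing to reproduce. The check compares the two definitions category by category.

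| Appendix 8 category | Counts in ORR (10.6.2, Appendix 8) | Counts in CBR as defined in 10.6.2 |
|---|---|---|
| CR | yes | yes |
| CRi | yes | no, not named |
| Refractory disease | no | no, not named |
| Progressive disease, relapse | no | no |
| Extramedullary PR | no | yes, if taken as the patient's status |
| Extramedullary No Response | no | no, not named |
| Stable disease | not in Appendix 8 | named, but cannot occur |

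Let n be the number of treated patients.

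- ORR = (CR + CRi)/n.
- CBR read literally = (CR + PR + SD)/n. For marrow disease PR = SD = 0, so CBR = CR/n.
- Difference on the same assessments: CBR − ORR = −CRi/n.
- With extramedullary disease: CBR − ORR = (extramedullary PR − CRi)/n. Any CRi not offset by an extramedullary PR puts CBR below ORR.

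**Illustration.** n = 20 is the arm size in the protocol's sample size text. The response counts are assumptions: 5 CR, 3 CRi, no extramedullary PR.

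- ORR = (5 + 3)/20 = 40% (Clopper-Pearson 95% interval 19.1% to 63.9%).
- CBR = 5/20 = 25% (8.7% to 49.1%).
- Difference = −3/20 = −15 percentage points.

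**Range over the unknown split.** With 8 responders of 20, ORR stays at 40%:

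| CRi among the 8 responders | 0 | 1 | 2 | 3 | 4 | 8 |
|---|---|---|---|---|---|---|
| Literal CBR | 40% | 35% | 30% | 25% | 20% | 0% |

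**Chance that the gap appears.** If each responder is CRi with probability p (assumed), the chance of at least one CRi among 8 is 1 − (1 − p)^8. This is 90% for p = 0.25 and 99.6% for p = 0.5.

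If CRi is added to the definition, CBR becomes (5 + 3)/20 = 40% and equals ORR for marrow disease.

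**The case against.** The best counter-argument is that the sentence is plainly a solid-tumour sentence. The endpoint list, the synopsis analysis text and the SAP all confine CBR to solid tumours, so nobody would compute it for leukaemia. For Part A this largely stands, because the SAP as written produces no such rate. It does not rescue 10.6.2, where T-ALL/T-LBL would then have a timetable and no definition. Section 10 defers each part's detail to an SAP finalised before database lock. That no Part B SAP is among these documents is not a defect, but nothing available corrects the heading for Part B.

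Some stronger readings are tempting and are not supported:

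- A reader might call the rate impossible or not computable. It can be computed, as shown above. A benefit rate below the response rate is also not impossible in itself: CBR is a status at a time point and ORR a confirmed best response, so relapse alone can produce the ordering. What is peculiar to T-ALL/T-LBL is that the CRi omission produces it on identical assessments.
- A reader might map refractory patients without progression to stable disease and obtain much higher rates. With six such patients added to the illustration, CBR would be (5 + 6)/20 = 55%, or (5 + 3 + 6)/20 = 70% with CRi as well. No text suggests that mapping. Refractory disease is an Appendix 8 category in its own right and, read literally, is not benefit.
- A reader might conclude that SAP section 6 wrongly declares no change from the protocol. SAP section 1 bases the SAP on protocol version 4.1 of 3 August 2020, whereas the protocol here is version 4.3 of 28 May 2021. The version 4.1 wording of 10.6.2 is not available, so a false statement is not shown.

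**Conclusion.** The point holds as a conflict within the protocol that yields a wrong result if followed. For marrow disease the literal shortfall of CBR against ORR is exactly the CRi proportion: 15 percentage points in the illustration, and anywhere from 0 to the whole of the ORR depending on the split. The direction follows from the definitions alone. The size rests on assumed counts and on there being no extramedullary PR to offset CRi.

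The consequence is limited. CBR is a secondary, descriptive result for one disease group. The T-ALL/T-LBL success criterion in section 10.5.2 uses the modelled response rate, so neither it, the primary endpoint nor the sample size is touched.

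**What to change.** Preferred: delete T-ALL/T-LBL and its timetable from the CBR heading in 10.6.2, so that the section agrees with the synopsis analysis text, section 4.2.2 and the SAP.

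Alternative, if a time-point rate is wanted for this disease:

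- Define it in Appendix 8 categories as the proportion of all treated T-ALL/T-LBL patients in CR or CRi.
- State how extramedullary PR and No Response count.
- Choose time points that follow the marrow schedule in the notes to the schedules of assessments (note 24 for Part A, note 21 for Part B). Those notes require marrow every 28 days until CR or CRi and allow 8-weekly assessment after confirmation. A fixed monthly grid would not match: a patient in remission on day 29 and confirmed on day 57 may next be assessed around day 57 + 56 = 113, with no marrow near day 85.
- Carry the definition into section 4.2.2 and the SAP for each part.

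Either route needs wording changes only and no new data. The small cost of deletion is that the T-ALL/T-LBL arm then has no CBR matching the solid-tumour arms in name.

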**Progression free survival (PFS) and overall survival (OS):**

Time from first treatment received until disease progression/overall survival will be summarised by Kaplan-Meier estimates, median PFS/OS and respective 95% CIs. Patients with no event will be censored at the last available tumour assessment for PFS and at the last timepoint known alive for OS.

**10.6.3 Pharmacokinetic Analyses**

CB-103 concentrations will be determined by a validated high-performance liquid chromatography (HPLC) tandem mass spectrometry (LC/MS/MS) method and the following PK parameters of CB-103 including:  $C_{max}$ ,  $t_{max}$ ,  $C_{min}$ ,  $C_{last}$ ,  $t_{last}$ ,  $AUC_{0-8}$ ,  $AUC_{0-24}$ ,  $AUC_{0-\infty}$ ,  $V_d/F$ ,  $V_{ss}/F$ ,  $CL/F$ ,  $t_{1/2}$  and AR. All pharmacokinetic parameters will be calculated from the curves constructed from the individual patients. Non-compartmental analysis will be performed using Phoenix WinNonlin version 6.3 (Pharsight Corporation, Mountain View, CA, USA).

No formal statistical analysis beyond descriptive statistics is planned. For each PK parameter, individual and mean data and summary statistics (including number of patients, arithmetic mean, geometric mean, standard deviation [StD], confidence value [CV], median, Min and Max) will be presented (note that for time to maximum plasma concentration [ $t_{max}$ ] and time to last measurable plasma concentration [ $t_{last}$ ] no geometric means will be calculated).

## **10.6.4 Pharmacokinetic / Pharmacodynamic Analyses**

With the PK timepoints collected, a population PK model will be built and then used to estimate individual AUCs or CL/F of CB-103. CB-103 AUC, as well as the observed  $C_{max}$ , will then be tested for association with signs of efficacy and safety. If an observable trend exists, a PK/PD model will be developed to evaluate the exposure-response relationship between CB-103 plasma exposure and outcome measures. Demographic and clinical data (ethnicity, current age, body weight, sex, disease status, etc.) will be utilised to assess interpatient variability in the PK and PK/PD relationships.

## **10.7 EXPLORATORY ANALYSES**

### **10.7.1 Additional PK, metabolite, PD markers, Genomic, Pharmacogenetics, and Protein Analyses, CB-103 metabolic expressions**

Exploratory PK assessments, plasma (or other matrix, e.g., urine) levels of metabolite(s), PD markers (genes, proteins) in tumour tissue biopsies and in whole blood, plasma samples and hair follicles, genotypes, protein expression and circulating tumour DNA in blood samples will be analysed as required by the Sponsor or by a delegated Laboratory or investigational site. A separate analysis plan and report for such assessments will be written.

### **10.7.2 Biomarker Analyses**

Summary statistics of PD, mechanistic and tumour profiling biomarkers will be reported by dose group and may be examined for possible correlations with CT/MRI/PET-CT efficacy endpoints. Additional analyses include comparing PD modulation with exposure.

### **10.7.3 CSF Exposure of CB-103 in Haematological Malignancies**

Summary statistics of the CB-103 concentration in CSF will be reported in selected patients with haematological malignancies. The concentrations in CSF will be compared with serum concentrations.

## **10.8 INTERIM ANALYSES**

### **10.8.1 Part A (Escalation)**

Each dose escalation step is considered to be an interim analysis. The BLRM will be updated with the respective number of patients treated and the number of DLTs observed in the last cohort. The updated model will then give a statistical recommendation for the next escalation step. However, a risk-benefit assessment that includes a comprehensive analysis of safety and available clinical information will be done to decide on the next escalation steps. The aggregate safety data from the additional patients in the MTD/RP2D confirmatory cohort will be continuously reviewed at least on a quarterly basis for all CTCAEs  $\geq$  grade 3, all SAEs, all clinically significant laboratory abnormalities and

available safety data, from all patients receiving RP2D, to confirm that the proposed dose for the expansion part is safe and well tolerated.

### **10.8.2 Part B (Expansion)**

Interim analyses will be triggered each time 10 patients in an arm have completed their first response assessment, this includes patients from the MTD/RP2D confirmatory cohort of Part A that qualify for any of the extension arms. An interim analysis will include all patients enrolled at, or prior to the cut-off (set by the completion of the 10th patient), and will be conducted once all patients have completed sufficient assessments to be categorised under the response endpoint, or have withdrawn from study. All arms that remain open to recruitment, and for which the minimum data efficacy requirements have been met, will be assessed for futility. For the interim and final analyses, a hierarchical model will be used. This model leads to more precise estimates of the indication-specific treatment effects as compared to those from stratified analyses. Details of the model can be found above and further descriptions are given in [Appendix 10](#). The results of the interim analyses will be non-binding. Safety criteria will also be evaluated to decide of the continuation of the study arms. Since this is a non-comparative multiple arm study no adjustment for multiple testing is made.

## **10.9 SAMPLE SIZE**

### **10.9.1 Part A - Dose Escalation and Dose Confirmation**

For all dose levels, from starting dose to the respective dose escalation levels, 3-6 patients will be enrolled and treated with CB-103 according to a staggered inclusion scheme to ensure adequate time for safety observation between inclusions, and before dose escalation. During the study, a minimum of 3 patients evaluable for the DDS will be treated per dose cohort until determination of the MTD or RP2D. Depending on the BLRM, additional patients may be enrolled in some dose cohorts. Approximately 11 dose cohorts are considered for this study with at least 3 patients per dose cohort. It is estimated that approximately 55 patients will be enrolled taking into account the drop-outs and additional patients enrolled for some of the dose groups. Based on the decision of the CRC approximately 45 patients in total may be enrolled on the MTD/RP2D confirmatory cohort to confirm safety before opening Part B.

### **10.9.2 Part B - Dose Expansion, Stratified by Indication**

Part B of the study will consist of one or several expansion arm(s) with selected tumour indications. For the analysis of the expansion arms a Bayesian Hierarchical binomial-design will be applied with enrolment of at least 10 patients into each arm. With 10-20 patients enrolled into each expansion arm it is estimated that about 100-140 patients (pending of the number of arms) will need to be recruited. Patients from the MTD/RP2D confirmatory cohort of Part A that qualify for any of the expansion arms will be included into the analyses of Part B and will contribute to the total sample size per arm.

20 patients per Indication arm will give sufficient evidence to determine early signs of clinical benefit. Assuming a true response rate of 30% for exchangeable and partially-exchangeable indications (based on response criteria) the lower limit of the credible band for the point estimate would be greater equal to 19%.

The following indications for patients with NOTCH activated pathway are considered and grouped into the respective expansion arms:

1. Adenoid cystic carcinoma (ACC)
2. Triple Negative Breast Cancer (TNBC)
3. Breast Cancer (ER+/-, HER2+/-)
4. Osteosarcoma, Malignant glomus tumour
5. GI cancers (resistant to oxaliplatin or irinotecan-based therapy colorectal cancer, hepatocellular carcinoma)
6. r/r T-ALL/T-LBL
7. Any other cancer (haematologic or solid) with confirmed Notch pathway activation (basket arm)

**Table 21** Sample size consideration for potential indications

	Indication				
	1.ACC	2.TNBC	3.Breast Cancer	4. Osteosarcoma, Malignant glomus tumour	5.GI
	n/N Median; (CI)	n/N Median; (CI)	n/N Median; (CI)	n/N Median; (CI)	n/N Median; (CI)
strong homogeneity	6/20 30% (18%-43%)	6/20 30% (18%-43%)	6/20 30% (18%-47%)	6/20 30% (18% - 43%)	6/20 30% (18%- 43%)

The indications considered for the expansion arms in Part B might be adapted and/or additional arms added by a protocol amendment based on the outcome of Part A and further findings from non-clinical studies with CB-103 and the planned interim analysis, this might increase the planned sample size.

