### **Part B (Expansion)**

Part B of the study will consist of one or several expansion arm(s) with selected tumour indications. For the analysis of the expansion arms a Bayesian Hierarchical binomial-design will be applied with enrolment of at least 10 patients into each arm. With 10-20 patients enrolled into each expansion arm it is estimated that about 100-140 patients (pending of the number of arms) will need to be recruited. Patients from the MTD/RP2D confirmatory cohort of Part A that qualify for any of the expansion arms will be included into the analyses of Part B and will contribute to the total sample size per arm.

20 patients per indication arm will give sufficient evidence to determine early signs of clinical benefit. Assuming a true response rate of 30% for exchangeable and partially-exchangeable indications (based on response criteria) the lower limit of the credible band for the point estimate would be greater than or equal to 19%.

The following indications for patients with NOTCH activated pathways are considered and grouped into the respective expansion arms:

1. Adenoid cystic carcinoma (ACC)
2. Triple negative breast cancer (TNBC)
3. Breast cancer (ER+/-, HER2+/-)
4. Osteosarcoma, Malignant glomus tumour
5. GI cancers (resistant to oxaliplatin or irinotecan-based therapy colorectal cancer, hepatocellular carcinoma)
6. r/r T-cell Acute Lymphoblastic Leukaemia (T-ALL) or T-cell Lymphoblastic Lymphoma (T-LBL)
7. Any other cancer (haematologic or solid) with confirmed Notch pathway activation (basket arm)

The indications considered for the expansion arms in Part B might be adapted and/or additional arms added by a protocol amendment based on the outcome of Part A and further findings from non-clinical studies with CB-103 and the planned interim analysis; this might increase the planned sample size.

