### 10.5.2 Part B (Expansion)

Once the MTD/RP2D is determined, enrolment into Part B (expansion) can be started by enrolling patients into several expansion arms for selected cancer indications. All patients in Part B will need to have tumours characterised by alterations and over-activation of the NOTCH signalling pathway (mutations, translocations, over-expressions).

For the primary analysis of the expansion arms a Bayesian hierarchical exchangeable binomial design will be used. The assumption of the model is that the true response rate in each of the preliminary indications for the Part B expansion arms is fully exchangeable.

For these indications the response criteria for success is a point estimate (from the model) above 25%.

The T-ALL/T-LBL indications are assumed to be only partially exchangeable with other indications. The success criteria for this indication is a point estimate (from the model) above 40%.

A robust hierarchical model (Neuenschwander et al., 2015) will be used for the analysis of the response rate  $p_k$  in the different indications  $k = 1, \dots, K$ . The number of responders in each indication follows a binomial likelihood function. For exchangeable indications ( $k = 1, \dots, K - 1$ ) it is assumed that

$$\text{logit}(p_k) \sim N(\mu, \tau^2)$$

On the other hand, for the partially (or non-) exchangeable indication  $K$  we use the mixture

$$\text{logit}(p_K) \sim N(\mu, \tau^2) \text{ with probability } \pi,$$

$$\text{logit}(p_K) \sim N(m, s^2) \text{ with probability } 1 - \pi$$

setting  $m = \text{logit}(0.3)$  and  $s = 2.2$ .

Further, the following weakly informative priors (Friede et al., 2016; Friede et al., 2017) are used:

$$\mu \sim N(\text{logit}(0.2), 2.5^2)$$

$$\tau \sim HN(1)$$

For these exchangeable indications, the advantage of this model is the fact that borrowing information across indications improves the precision of the estimators of the response rate. On the other hand, for the possibly different indication, the mixture approach hedges for a too-optimistic assumption about similarity. Therefore, the described approach captures the design adequately.

Other characterisations of the posterior distribution will be evaluated as appropriate. The final analysis will take place after the last expansion arm was closed for futility or the last patient of the last expansion arm had the final end-of-study visit.

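### Part B's lower credible limit of at least 19% depends on 6/20 in every arm and on the number of arms; it is unsupported for T-ALL/T-LBL while pi is unstated, and one Table 21 cell is wrong

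*Protocol*

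**What the plan says.** Protocol 10.9.2 justifies the arm size with "20 patients per Indication arm will give sufficient evidence to determine early signs of clinical benefit". The next sentence gives the only numerical precision for that size. It starts "Assuming a true response rate of 30% for exchangeable and partially-exchangeable indications (based on response criteria" and concludes that "the lower limit of the credible band for the point estimate would be greater equal to 19" per cent. The synopsis, under the Part B sample size, repeats it: "the lower limit of the credible band for the point estimate would be greater than or equal to 19" per cent.

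The number of arms is left open: "Part B of the study will consist of one or several expansion arm(s) with selected tumour indications". Seven are then listed, the last being "Any other cancer (haematologic or solid) with confirmed Notch pathway activation (basket arm". Table 21, in the same section, has five columns, each with 6/20 and a median of 30%. Four cells give 18%-43% and Breast Cancer gives 18%-47%. T-ALL/T-LBL and the basket arm have no column.

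Section 10.5.2 treats the other indications as fully exchangeable, but "The T-ALL/T-LBL indications are assumed to be only partially exchangeable with other indications". T-ALL/T-LBL therefore follows a two-part mixture: weight pi on the common distribution and 1 − pi on a stand-alone one. No value is given for pi.

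**The concern.** The sentence says at least 19%, yet every cell of the table beside it prints a lower limit of 18%. The sentence also gives T-ALL/T-LBL the same precision as the solid-tumour arms, although that arm is modelled so as to borrow less. It starts from a true rate, whereas the table starts from an observed count. And identical data in exchangeable arms cannot yield two different intervals.

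What is at stake is the stated precision behind 20 patients per arm. A reader would expect T-ALL/T-LBL to be estimated as tightly as the other arms, and would expect a 19% limit whenever the true rate is 30%.

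**Working it through.** **Inputs.** From Section 10.5.2: logit(p_k) ~ N(mu, tau²) for exchangeable arms; mu ~ N(logit 0.2, 2.5²); tau ~ half-normal(1); for T-ALL/T-LBL, N(mu, tau²) with probability pi and N(logit 0.3, 2.2²) with probability 1 − pi. From Section 10.9.2: 20 patients per arm and a 30% rate, so 0.30 × 20 = 6 responders expected.

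Assumptions: intervals are equal-tailed 95%, because no level is stated; pi is varied from 0 to 1, because no value is stated.

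**Formulas.** An exchangeable arm contributes L_k(mu, tau) = ∫ Bin(y_k; n_k, expit θ) N(θ; mu, tau²) dθ. T-ALL/T-LBL contributes pi × L(mu, tau) + (1 − pi) × ∫ Bin(y; n, expit θ) N(θ; logit 0.3, 2.2²) dθ. The posterior of (mu, tau) is proportional to the priors times the product of these terms. It was integrated numerically. Different grids, and a separate MCMC run, moved the limits by about 0.1 to 0.2 points.

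**Reproducing the plan's own figures.**
- Appendix 10 Table 4, final analysis, high response, ACC 7/20: 28.9% (17.3%-46.3%); printed 29% (17%-46%).
- Same table, strong heterogeneity, GI 11/20: 47.0% (25.8%-69.1%); printed 47% (26%-69%).
- Table 21, five exchangeable arms at 6/20: 18.4%-43.0%; printed 18%-43% in four cells. A 90% interval would give a lower limit of 20.3%, so 95% is the level that fits.

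**Step 1: exchangeable arms only, 6/20 in each.**

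| Arms | 1 | 2 | 3 | 4 | 5 | 6 | 7 |
|---|---|---|---|---|---|---|---|
| Lower limit | 12.6% | 14.7% | 16.2% | 17.4% | 18.4% | 19.2% | 19.9% |

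The text's 19% and the table's 18% come from the same model with different numbers of arms.

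**Step 2: the listed layout, six exchangeable arms plus T-ALL/T-LBL, 6/20 in each.**

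| pi | Exchangeable arm, lower limit | T-ALL/T-LBL, lower limit |
|---|---|---|
| 0 | 19.2% | 13.0% |
| 0.25 | 19.6% | 15.3% |
| 0.5 | 19.7% | 17.3% |
| 0.75 | 19.8% | 18.9% |
| 1 | 19.9% | 19.9% |

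The exchangeable arms meet 19% at every pi. T-ALL/T-LBL reaches 19.0% at pi of about 0.77, or 18.5% (which rounds to 19%) at about 0.68. At pi = 0.5 its interval is about 17%-44%, against 20%-41% for an exchangeable arm.

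**Step 3: a true rate of 30% instead of an observed 6/20.** Counts were drawn at a true 30% in all seven arms, with 20 patients each, for 5,000 trials (simulation error about 0.7 points). An exchangeable arm's limit was at least 19% in 37% (pi = 0), 40% (0.5) and 41% (1) of trials. For T-ALL/T-LBL it was 23%, 30% and 40%. A smaller run of 400 trials per pi gave 39% and 44% for an exchangeable arm at pi of 0.5 and 1. Counting 18.5% as 19% still leaves every figure below one half.

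**Step 4: the Breast Cancer cell.** All five columns of Table 21 have 6/20 and are exchangeable under one model, so the five posteriors are identical by symmetry. The common interval is 18%-43%; 47% cannot be right.

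**The case against.** The best defence has four parts.

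- **The figure is right for the arms the protocol lists.** With seven arms and 6/20 throughout, exchangeable arms do reach 19%. This stands. A reader might infer from the 18% in Table 21 that the 19% was miscalculated. It was not: neither the sentence nor the table states its number of arms.
- **Pi is unknown, so the T-ALL/T-LBL claim is not shown to be false.** This also stands. The SAP supplied covers Part A only and Protocol Section 10 foresees a SAP for each part, so pi may be fixed elsewhere. But a claim that needs pi of about 0.77 or more, in a protocol that gives no pi and no T-ALL/T-LBL row in Table 21 or in the Part B tables of Appendix 10, is unsupported as written.
- **Precision is usually evaluated at the expected count.** Table 21 does so, and the protocol promises no frequency over repeated trials. A reader might take the four-in-ten result as a second arithmetic error. It is not one; it shows only that the sentence should be conditioned on 6/20 and not on a true rate.
- **Nothing is decided on the lower limit.** Success is a point estimate above 25%, or above 40% for T-ALL/T-LBL, and interim results are non-binding. This stands and limits the consequence, but the sentence is still the stated reason for 20 patients per arm.

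**Conclusion.** The precision statement needs restating. It is sound for exchangeable arms in the listed seven-arm layout if 6/20 is observed in every arm (19.2% to 19.9% for any pi). It becomes 18% with five arms and falls to 12.6% with one. For T-ALL/T-LBL beside six arms at 6/20 it is unsupported: about 13% to 18.9% for pi up to 0.75, reaching 19% only at about 0.77, or about 0.68 with rounding. The condition should be the observed count, since a true 30% rate brings an exchangeable arm to 19% in only about four trials in ten. The 47% in Table 21 is inconsistent with the model whatever value pi takes.

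These results rest on 95% equal-tailed intervals, which reproduce the plan's tables, and on the full range of pi with no value preferred. It would be going too far to conclude that Part B is too small or that its success rules are affected. The documents tie neither to this limit, and Part B is exploratory and non-comparative.

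**What to change.** 1. In the synopsis and in 10.9.2, make the sentence conditional on 6 of 20 responding in every arm, and name the number of arms and pi. For an exchangeable arm the 95% interval is about 18%-43% with five arms and 19%-42% with six. In the listed layout of six plus T-ALL/T-LBL it runs from 19%-42% at pi = 0 to 20%-41% at pi of 0.5 or more.
2. State pi, and give T-ALL/T-LBL its own interval at that value (for example about 17%-44% at pi = 0.5 beside six other arms). Keep the arm under the 19% claim only if the chosen pi supports it.
3. Label Table 21 as a five-arm layout and correct the Breast Cancer upper limit from 47% to 43%.

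The cost is one re-run of the existing model and a few edited lines. The stated precision becomes less favourable for layouts of five or fewer arms, and for T-ALL/T-LBL unless pi is high. No patient number or decision rule changes.
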